4.1.3 Exploratory Endpoints

[REDACTED]

[REDACTED]

4.2 Safety Endpoints

Beside the evaluations used to address the primary endpoint of the DLT evaluation period (the incidence of DLTs), safety endpoints include deaths, SAEs and AEs, select AEs, immune-mediated AEs (IMAEs), and other events of special interest, laboratory evaluations, electrocardiograms (ECG), and reasons off treatment.

4.2.1 Select Adverse Events

The select Adverse Events (select AEs) consist of a list of preferred terms grouped by specific category that are of relevance for understanding the risks of immune therapies such as nivolumab. To date, 7 categories of select AEs have been identified see Table 4.2.1-1.

Table 4.2.1-1: Select Adverse Events

Category	Subcategory
Endocrine Adverse Events	Adrenal Disorder
	Diabetes
	Pituitary Disorder
	Thyroid Disorder
Hypersensitivity/Infusion Reactions	
Gastrointestinal Adverse Events	
Hepatic Adverse Events	
Pulmonary Adverse Events	
Renal Adverse Events	
Skin Adverse Events	

AEs that may differ from or be more severe than AEs caused by non-immunotherapies and AEs whose early recognition and management may mitigate severe toxicity are included as select AEs. The select AEs and the categories are defined by the Sponsor and the list that is the most current at the time of analysis will be used. Changes may be made to this list with each new version of the Medical Dictionary for Regulatory Activities (MedDRA), prior to database lock. Categories of select AEs may include subcategories (e.g. adrenal disorders, diabetes, pituitary disorders, and thyroid disorders are subcategories of the endocrine event category). Other categories could be created during the conduct of the study. If so, similar table/listing will be produced for these

additional categories. Similarly, some category can be removed or regrouped and corresponding table/listing will be updated accordingly.

The analysis of select adverse events will be conducted using the 30-day safety window.

4.2.2 Immune-mediated Adverse Events

In order to further characterize the safety profile of immune therapies such as nivolumab, an analysis of immune-mediated AEs (IMAE) will be conducted. IMAEs are specific events (or groups of PTs describing specific events) that include pneumonitis, diarrhea/colitis, hepatitis, nephritis/renal dysfunction, rash, and endocrine events (hypothyroidism/thyroiditis, hyperthyroidism, hypophysitis, diabetes mellitus, adrenal insufficiency). In addition, hypersensitivity/infusion-related reactions will be analyzed along with the IMAE categories because multiple event terms may be used to describe such events and pooling of terms is therefore necessary for full characterization. Hypersensitivity/infusion-related reactions do not otherwise meet criteria to be considered IMAEs.

IMAE analyses include events, regardless of causality, occurring within 100 days of the last dose. Related analyses are limited to subjects who received immunosuppressive medication for treatment of the event, with the exception of endocrine events which will be included regardless of treatment since these events are often managed without immunosuppression. IMAE categories will be populated using the list that is the most current at the time of analysis.

4.2.3 Other Events of Special Interest

The other events of special interest (OESI) consist of a list of preferred terms grouped by specific category (i.e.: myasthenic syndrome, demyelination, Guillain-Barre syndrome, pancreatitis, uveitis and encephalitis). The OESI categories and terms are defined by the Sponsor and the list that is the most current at the time of analysis will be used.

[REDACTED]

[REDACTED]

[REDACTED]

[REDACTED]

[REDACTED]

[REDACTED]

[REDACTED]

[REDACTED]

[REDACTED]

[REDACTED]

[REDACTED]

[REDACTED]

[REDACTED]

[REDACTED]

[REDACTED]

[REDACTED]

[REDACTED]

[REDACTED]

[REDACTED]

[REDACTED]

[REDACTED]

[REDACTED]

[REDACTED]

[REDACTED]

[REDACTED]

[REDACTED]

[REDACTED]

5 SAMPLE SIZE AND POWER

Within each tumor type, the sample size will start with a minimum of 3 treated subjects using a Rolling Six design for evaluation of DLT. Then, the sample size will be increased by the number of subjects needed to continue the DLT evaluation then, by the number of subjects needed for one or three randomized cohort(s) to complete the Dose Evaluation Phase. Finally, the sample size will be increased by the number of subjects needed for the Dose Expansion Phase.

5.1 SCLC Sample Size

For SCLC, up to approximately 175 treated subjects may be needed. This sample size considers the following:

- Up to 18 subjects for the DLT evaluation
- 19 subjects per cohort for the Dose Evaluation Phase (57 subjects for three randomized cohorts)
- A second stage of a Simon 2-stage like design in the Dose Expansion Phase that would require an additional 25 subjects

OR

- A randomized Phase 2 study with comparative arm in the Dose Expansion Phase that would require an additional 50 subjects per arm (i.e. 100 for the two arms)

These numbers are obtained using the following methods and assumptions:

- A Simon optimal 2-stage design will test the null hypothesis that the true response rate is less than or equal to 15% versus the alternative hypothesis that it exceeds 15%. The type I error rate will be 5% (one-sided) and the design will have 90% power to reject the null hypothesis when the true response rate is 35%. The Simon design in this tumor type will require 19 treated subjects for the first stage and at least 4 responders to initiate Stage 2. An additional 25 treated subjects will be needed for the second stage and the drug will be considered of potential clinical interest if, at the end of the second stage, there are 11 or more responders out of the total of 44 treated subjects. Subjects who were assigned treatment but never treated will not count towards the total of 19 treated subjects for the first stage or the 44 treated subjects in a cohort and will be replaced.
- If an open label randomized Phase 2 with comparative arm study is initiated (1:1 ratio), the primary measurement for efficacy will be IRRC assessed ORR. Considering one-sided alpha level of 0.10 a sample size of 50 subjects per arm would provide approximately 80% power to detect a difference of 20% in the response rates between the two arms (based on a Fisher's exact test) assuming an ORR of 35% for the combination arm of ulocuplumab plus nivolumab and an ORR of 15% for the nivolumab monotherapy arm.

5.2 PAC Sample Size

For PAC, up to approximately 331 treated subjects may be needed. This sample size considers the following:

- Up to 18 subjects for the DLT evaluation
- 21 subjects per cohort for the Dose Evaluation Phase (63 subjects for three randomized cohorts)
- A second stage of a Simon 2-stage like design in the Dose Expansion Phase that would require an additional 20 subjects

OR

- A randomized Phase 2 study with comparative arm in the Dose Expansion Phase that would require an additional 125 subjects per arm (i.e. 250 for the two arms)

These numbers are obtained using the following methods and assumptions:

- A Simon optimal 2-stage design will test the null hypothesis that the true response rate is less than or equal to 5% versus the alternative hypothesis that it exceeds 5%. The type I error rate will be 5% (one-sided) and the design will have 90% power to reject the null hypothesis when the true response rate is 20%. The Simon design in this tumor type will require 21 treated subjects for the first stage and at least 2 responders to initiate Stage 2. An additional 20 treated subjects will be needed for the second stage and the drug will be considered of potential clinical interest if, at the end of the second stage, there are 5 or more responders out of the total of 41 treated subjects. Subjects who were assigned treatment but never treated will not count towards the total of 21 treated subjects for the first stage or the total of 41 subjects in a cohort and will be replaced.
- If an open label randomized Phase 2 study with comparative arm is initiated (1:1 ratio), the primary measurement for efficacy will be OS. A one-sided alpha level of 0.10 log-rank test will be used to compare the OS of subjects randomized to the combination arm of ulocuplumab plus nivolumab to that of subjects randomized to the investigator's choice chemotherapy arm. In order for the test to have at least 80% power to reject the null hypothesis of no difference in OS among treatment groups when the hazard ratio of the experimental arm to the control arm is 0.75, the study will require 218 events (deaths) to complete. The analysis of OS will take place when the following two conditions have been met: 218 events have been observed and all subjects have been on study for at least 6 months. The requirement that subjects be on study for at least 6 months is meant to ensure adequate follow-up. A total of 250 subjects are to be randomized. Assuming an accrual rate of 20 subjects per month, the accrual will last approximately 13 months. Assuming exponentially distributed OS and median OS times in the control and experimental arms of 4.5 months and 6.0 months, respectively, it is expected that the requisite number of events (deaths) will occur approximately 10 months after all subjects have been randomized.

6 STUDY PERIODS, TREATMENT REGIMENS AND POPULATIONS FOR ANALYSES

6.1 Study Periods

6.1.1 Baseline Period

- Baseline AEs will be defined as AEs with an onset date prior to but not including the first day of treatment.

- For infusion related events, baseline will be defined as AEs with an onset date and time prior to but not including the first day and time of treatment.
- For all other evaluations (ECOG, laboratory data, ECGs, vital signs, etc.) baseline will be defined as evaluations with an onset date on or prior to the first day of treatment.

If there are multiple valid assessments, the assessment that is closest to day (and time if collected) of the first dose of study treatment will be used as the baseline in the analyses. If multiple assessments are collected on the same date (and time, if collected), the assessment with the latest database entry date (and time, if collected) will be considered as baseline.

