## **5.3 Safety Assessments**

Safety assessments should be performed per tables in [Section 5.1](#).

Physical examinations are to be performed per tables in Section 5.1 and as clinically indicated. If there are any new or worsening clinically significant changes since the last exam, report changes on the appropriate non-serious or serious adverse event page.

Women of childbearing potential (WOCBP) must have a negative serum or urine pregnancy test (minimum sensitivity 25 IU/L or equivalent units of HCG) within 24 hours prior to the start of study drug and at time points specified in Section 5.1. Chest X-ray is to be performed for monitoring of pulmonary toxicity per tables in Section 5.1.

Additional measures, including non-study required laboratory tests, should be performed as clinically indicated or to comply with local regulations. Laboratory toxicities (eg, suspected drug induced liver enzyme elevations) will be monitored during the follow-up phase via on site/local labs until all study drug-related toxicities resolve, return to baseline or are deemed irreversible.

Vital signs should be assessed at each on-study visit prior to dosing. Vital signs should also be taken as per institutional standard of care prior to, during and after dosing. Oxygen saturation by pulse oximetry should be obtained prior to dosing and at any time a subject has any new or worsening respiratory symptoms. A reading at rest should be obtained at each time point. If a subject shows changes on pulse oximetry or other pulmonary related signs (eg, hypoxia, fever) or symptoms (eg, dyspnea, cough) consistent with possible pulmonary adverse events, the patient

subject should be immediately evaluated to rule out pulmonary toxicity. An algorithm for the management of suspected pulmonary toxicity can be found in [Appendix 2](#).

Some of the previously referred to assessments may not be captured as data in the eCRF. They are intended to be used as safety monitoring by the treating physician. Additional testing or assessments may be performed as clinically necessary or where required by institutional or local regulations.

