6.1.2 Post Baseline Period

- On-treatment AEs will be defined as AEs with an onset date on or after the first day of treatment.
- For infusion related events, on-treatment will be defined as AEs with an onset date and time on or after the first day and time of treatment.
- For all other evaluations (ECOG, laboratory data, ECGs, vital signs, etc.) on-treatment will be defined as evaluations taken after the first day of treatment.
- If a subject is still on study treatment, any AE/evaluation post baseline is considered as on-treatment. For subjects off study treatment, AEs/evaluations will be counted as on-treatment if the event occurred within 30 days or 100 days (depending on the analysis) after the last dose of ulocuplumab or nivolumab, whichever is later.
- Late-emergent drug-related AEs will be defined as drug-related AEs with an onset date greater than 100 days after the last dose of study treatment in subjects who are off study treatment.

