7.6.12 Clinical Laboratory Evaluations

7.6.12.1 Hematology, Serum Chemistry, and Electrolytes

Thrombocytopenia will mainly be examined using laboratory data. Analyses on hematology, serum chemistry, and electrolytes will consist of the followings:

- Worst CTC grade on-treatment per subject,
- Shift table of worst on-treatment CTC grade compared to baseline CTC grade per subject.

For each analysis, the following laboratory tests will be summarized:

- Hematology: hemoglobin (HB), platelets, white blood counts (WBC), absolute neutrophils count (ANC) and absolute lymphocyte count (LYMPA).
- Serum chemistry: alanine aminotransferase (ALT), aspartate aminotransferase (AST), alkaline phosphatase (ALP), total bilirubin and creatinine.

- Electrolytes: sodium (high and low), potassium (high and low), calcium (high and low), magnesium (high and low).
- Other: amylase (AMYL) and lipase (LIPA and LIPAC, lipase by colorimetric assay).

The analyses will be conducted using the 100-day safety window.

Listing of these laboratory parameters will be provided.

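### The SAP's date-based baseline rule lets an unscheduled Day 1 post-dose laboratory value become baseline, which can hide a shift in the laboratory tables

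*SAP*

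**What the plan says.** SAP 6.1.1 (Baseline Period) has three rules. Adverse events are baseline if they start before the first treatment day. Infusion-related events use date and time: "baseline will be defined as AEs with an onset date and time prior to but not including the first day and time of treatment". Every remaining kind of measurement, such as performance status, laboratory values, ECGs and vital signs, is handled by date alone: "baseline will be defined as evaluations with an onset date on or prior to the first day of treatment".

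Where several valid assessments qualify, "the assessment that is closest to day (and time if collected) of the first dose of study treatment will be used as the baseline". Where date and time (if collected) coincide, "the assessment with the latest database entry date (and time, if collected) will be considered as baseline".

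SAP 6.1.2 (Post Baseline Period) says of the same evaluations that "on-treatment will be defined as evaluations taken after the first day of treatment". A later bullet in that section adds: "If a subject is still on study treatment, any AE/evaluation post baseline is considered as on-treatment".

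The visible output that relies most directly on both definitions is in SAP 7.6.12.1: worst on-treatment grade per subject, and "Shift table of worst on-treatment CTC grade compared to baseline CTC grade per subject".

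**The concern.** A baseline value should describe the subject before exposure. The rule for non-AE evaluations works on the calendar date, so a Day 1 value is eligible whether it was taken before or after the infusion. The selection rule measures distance from the dose without regard to direction. Mention of time, where collected, sharpens the distance but does not require the value to come first. If times are missing, the order of data entry can decide which value is the baseline.

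A post-dose value chosen this way does damage twice in the shift table. It raises the starting grade, and it is missing from the on-treatment values over which the worst grade is taken. Both act in the same direction, toward showing no worsening. The SAP already writes a strict date-and-time rule for infusion-related events, so the looser rule for measurements looks like an oversight. The point carries some weight for haematology, because SAP 7.6.12.1 says that low platelets will be examined mainly through laboratory data.

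**Working it through.** No power, alpha or event count is involved, and the plan states no figure to reproduce. The check applies the two SAP sections literally to constructed cases.

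**Inputs from the documents**
- Baseline window: dated on or before Day 1 (SAP 6.1.1).
- Selection: smallest distance from the first dose, direction not stated; ties go to the latest database entry (SAP 6.1.1).
- On-treatment window: after Day 1 (SAP 6.1.2).
- Scheduled laboratory tests: within 72 hours before dosing (Protocol Tables 5.1-2, 5.1-3 and 5.1-4). Screening tests done within 72 hours before the first dose may serve for Day 1 (Protocol Table 5.1-1).
- Additional laboratory tests may be done as clinically indicated (Protocol 5.3), so unscheduled samples are possible.

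**Assumed for illustration:** the sample times and the grades. One subject has Grade 1 ALT before dosing, Grade 3 in an unscheduled sample after the infusion starts, and Grade 1 after recovery.

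**Case A, times collected.** Pre-dose sample 48 h before the dose, unscheduled sample 2 h after. Both fall in the baseline window. Distances are 48 h and 2 h. Since 2 < 48, the post-dose value is baseline.
- SAP rule: baseline Grade 3, worst on-treatment Grade 1, no worsening.
- Pre-dose rule: baseline Grade 1, worst on-treatment Grade 3, a rise of two grades.

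**Case B, times not collected, pre-dose sample on an earlier day.** The 72-hour window allows this. The Day 1 sample is nearer by day, so the post-dose value is again baseline, with the same result as Case A.

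**Case C, times not collected, both samples on Day 1.** They tie. Whichever was entered later becomes baseline, so the reported shift depends on data entry.

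**Case D, times collected, pre-dose sample 1 h before and unscheduled sample 2 h after.** Since 1 < 2, the pre-dose value is correctly baseline. The post-dose value is not dated after Day 1, so the specific on-treatment definition leaves it out. The later bullet on post-baseline evaluations could be read to bring it back. The SAP is ambiguous here.

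In Cases A and B the rule gives the wrong table entry. In Case C it may. In Case D the baseline is right and the on-treatment status is unclear. None of the cases arises if the only Day 1 sample was taken before the dose, which is what the protocol schedules.

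**The case against.** The strongest reply is that the rule will seldom bite, and most of that reply stands.

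- **Scheduled laboratory tests are pre-dose.** Only an unscheduled Day 1 post-dose sample creates the problem. That a site would draw one during a reaction is plausible, but the documents do not say that it will happen.
- **Safety reporting has other routes.** Adverse events starting on Day 1 are on-treatment, and infusion-related events use date and time (SAP 6.1.2). Protocol 6.3 requires AE or SAE capture of a laboratory abnormality that is clinically significant, needs corrective therapy, or leads to delay or discontinuation. A Grade 3 value during a reaction would ordinarily appear in the AE tables.
- **The rule may be completed elsewhere.** The word *valid* in SAP 6.1.1 is undefined, and SAP Section 8 sends conventions to a Data Presentation Plan that is not among the documents. A pre-dose restriction could sit there.
- **The later bullet in SAP 6.1.2** may rescue a Day 1 value that was not chosen as baseline. A reader might infer that every Day 1 value is barred from the on-treatment set. The text is ambiguous on that and does not establish it.

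A reader might also infer that vital signs and tumour or inflammation markers are affected. Protocol 5.3 does say "Vital signs should also be taken as per institutional standard of care prior to, during and after dosing", and CRP and CA19.9 are scheduled on Day 1 without a pre-dose instruction. But Protocol 5.3 also warns that some assessments may not reach the eCRF. The SAP's section on vital signs is visible only in its contents list, and no visible SAP analysis uses CRP or CA19.9. No effect on those analyses can be shown.

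These points limit how often the problem occurs. None of them makes the baseline choice in Cases A to C correct.

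**Conclusion.** The concern holds for laboratory data. As written, SAP 6.1.1 and 6.1.2 allow an unscheduled Day 1 post-dose value to be taken as baseline and left out of the worst on-treatment grade, which hides a shift in the tables of SAP 7.6.12.1. In the worked example a two-grade rise is reported as no worsening.

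The reach is narrow: probably a changed table cell for an occasional subject. The frequency cannot be computed, because the documents do not say how many unscheduled Day 1 samples are expected or whether times are recorded. The conclusion assumes that such samples reach the database and that the Data Presentation Plan does not already impose a pre-dose condition.

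A reader might go further and infer that first-dose toxicity disappears from the study, or that dose decisions are at risk. The documents do not support that. AE analyses count Day 1 events. The DLT criteria do refer to baseline liver tests, but DLTs are judged from drug-related events and laboratory abnormalities over the first 6 weeks, and nothing ties them to the shift-table derivation. ORR and PFS rest on tumour assessments and do not use this rule.

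**What to change.** 1. **SAP 6.1.1:** for non-AE evaluations, define baseline as the last non-missing value before the start of the first infusion, by date and time where time is collected. Where it is not, let Day 1 values that the protocol schedules as pre-dose be eligible, and do not use unscheduled Day 1 values as baseline.
2. **SAP 6.1.2:** count Day 1 values known to follow the start of the first infusion as on-treatment, and make the later bullet on post-baseline evaluations agree. Unscheduled Day 1 values of unknown timing would then fall in neither set; the listing already planned in SAP 7.6.12.1 can show them.
3. **Tie-break:** replace database entry order with the latest pre-dose collection time, or the mean if times are identical. The worst value should not be used, because it would raise the baseline grade and hide worsening, the same fault as now.
4. If the Data Presentation Plan already contains a pre-dose rule, state it in these two sections.

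The cost is SAP wording and a small programming change. How fully it can be applied depends on whether times are recorded: the SAP says only that time is used if collected, so this should be checked against the CRF. No new assessments are needed.

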6.1.2 Post Baseline Period

- On-treatment AEs will be defined as AEs with an onset date on or after the first day of treatment.
- For infusion related events, on-treatment will be defined as AEs with an onset date and time on or after the first day and time of treatment.
- For all other evaluations (ECOG, laboratory data, ECGs, vital signs, etc.) on-treatment will be defined as evaluations taken after the first day of treatment.
- If a subject is still on study treatment, any AE/evaluation post baseline is considered as on-treatment. For subjects off study treatment, AEs/evaluations will be counted as on-treatment if the event occurred within 30 days or 100 days (depending on the analysis) after the last dose of ulocuplumab or nivolumab, whichever is later.
- Late-emergent drug-related AEs will be defined as drug-related AEs with an onset date greater than 100 days after the last dose of study treatment in subjects who are off study treatment.

